### 3.5 Retention Rates

The study is an intention to treat analysis and therefore if a patient does not apply the TENS or attend the education class (if randomised to this arm) they will continue to be followed up. However, all participants will have the right to withdraw from the study at any stage. If willing the reasons for withdrawal will be documented and any data already collected from that participant will be analysed.

## 4 Trial procedures

**Study design:** This is a double-blind, feasibility RCT. TENS/placebo and patient education interventions will be 6 weeks in duration and all participants will receive secondary prevention therapy as recommended by NICE including advice to exercise (usual care). A sub-group of participants (those recruited within the first 8 months of recruitment) will be followed up for 3 months post-intervention. A qualitative, focus group study will also be conducted after final follow up.

### Interventions:

**TENS:** Participants will be given TENS at intervention visit. They will be instructed to use the device daily at home or elsewhere. They will be specifically advised to use the device prior to, or during, a challenging walk each day. Challenging walk could be for activities of daily living (ADL) or planned exercise. For those with bilateral claudication they are advised to wear the device on the worst limb and could alternate it as symptoms fluctuates. The active group will receive High Frequency-TENS (120 Hz, 200µs and a patient-determined intensity of “strong but comfortable”).

**Placebo TENS:** Participants will receive the same model and instructions for use as those in the active group except that the stimulation dose is be safely altered to produce non-therapeutic, ineffective stimulation. For the purposes of blinding, participants will be told that different dosages of TENS are being tested some of which they might not feel anything even though the device is working. This method of effecting placebo has been successfully used in previous TENS trials.

Both the statistician conducting the randomization and the outcome assessor would be blinded to active TENS and placebo TENS. Importantly, participants will receive the same set of instructions as those in active TENS with the addition of a statement that two TENS are being tested. Blinding will be assessed at the end of the intervention period. Participants will be asked if they believed their TENS unit was functioning properly.

**Patient-Centred Education:** Intervention in these groups will be adopted from the successfully piloted SEDRIC study: A one-off three-hour workshop of structured group education (4-5 persons in each group) and three 2-weekly phone calls. Two educators will implement the session. Training for educators will involve completion of the DESMOND core training, reading and demonstrating understanding of the SEDRIC curriculum, and completion of at least two practice workshops that are

quality assessed prior to delivering any sessions to patients. The aim of the patient education will be to modify patients' illness beliefs and perceptions about IC/PAD by educating them on disease pathology and self-management philosophy. After the workshop, each patient will be supported to set goals for walking using the pedometer (Yamax SW-200 Digi-Walker pedometers), develop an action plan regarding how these goals will be met and encouraged to repeat this process for each new walking goal. See SEDRIC curriculum for details.

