Methodology:	This a randomised controlled feasibility trial using a 2x2 factorial design of TENS versus placebo TENS with or without patient-centred education. Participants will be blinded to the type of TENS they receive. Outcome assessment of the primary outcome will be done by a blinded assessor.
Sample Size:	80
Screening:	Participants will be screened for eligibility by Research Nurse
Registration/Randomisation:	Randomisation by Robertson Centre for Biostatistics
Main Inclusion Criteria:	
 
• Clinical diagnosis of symptomatic Peripheral Arterial Disease (PAD) including resting ABPI <0.9 in at least one leg
 

	
 
• Stable IC for <math>\geq 3</math> months
 
• Walking limited primarily by claudication
 
• Able to exercise on a treadmill
 
• Able to read and speak English to a level allowing satisfactory completion of the study procedures
 
• Able to provide written informed consent for participation
 

Main Exclusion Criteria:	
 
• Planned surgical or endovascular intervention for PAD within the next 3 months
 
• Critical limb ischaemia
 
• The presence of any absolute contraindications to exercise testing/training as defined by the American College of Sports Medicine (ACSM)
 
• Previous experience of using TENS/ structured patient education for PAD
 
• Contraindications to TENS (including epilepsy, dermatological conditions, indwelling electrical pumps/pacemakers) and inability to apply TENS independently.
 
• Patients who require walking aids including artificial limbs
 
• Major surgery, myocardial infarction or stroke/ TIA in the previous 6 months
 
• Co-morbidities that cause pain or limit walking to a greater extent than IC (e.g. severe arthritis)
 
• <math>>20\%</math> variation in baseline ACD on treadmill
 
• Severe peripheral neuropathies above the ankle.
 
• Participation in another research protocol
 
• Participants <math>< 40</math> years of age
 

Product, Dose, Modes of Administration:	One-off 3 hours structured patient education + twice weekly phone call follow up to six weeks; High frequency TENS for daily use up to six weeks; placebo TENS for daily use for six weeks
Duration of Treatment:	Six weeks

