### Visit 2- Second Assessment Visit (usually within 2 weeks after visit 1):

Participants will then attend for a second visit to undergo a second Treadmill test, and to return the activPAL and sleep diary. Only participants with ≤20% variation in ACD will continue in the trial. After this visit eligible participants will be randomized, and given a date for them to return for intervention (TENS/Placebo ± Education) as applicable. Recruitment and randomisation will be done in waves to allow groups to be formed for the education session.

Second Assessment Visit (30 mins)	Time (mins)	Responsible
Return of ActivPAL by participants	5	RN/UA
Treadmill protocol • McGill Pain Questionnaire (5 minutes after completion of the treadmill protocol)	20	

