## 6.2 Placebo TENS:

Placebo effect has been reported while using TENS in other conditions therefore, testing active TENS against placebo is advocated. The same model as used in active TENS will be used in the placebo TENS group but an infective setting (current intensity of about 6mA) will be used. Patients will be told that different doses of TENS are being tested. This will allow the unit to be switched on with the appearance of a working unit. All TENS units will be calibrated, checked and confirmed prior to being issued to participants. This method of achieving placebo has been successfully used in previous TENS trials.

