#### **14.2 Informed consent**

Written informed consent shall be obtained from each trial participant. The Research Nurse will explain the exact nature of the study in writing, provision of patient information sheet, and verbally and will be responsible for consenting the participants. Trial participants will be informed that they are free to withdraw their consent from the study or study treatment at any time.

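### Section 4 of the protocol, read literally, adds a statement to the placebo TENS instructions only; it should give one script to all four groups

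*Protocol*

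**What the plan says.** The Placebo TENS text in protocol section 4 (Interventions) describes what these participants are told in three places.

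- It opens with "Participants will receive the same model and instructions for use as those in the active group", and the only stated exception is the stimulation dose.
- It then says that, for blinding, "participants will be told that different dosages of TENS are being tested some of which they might not feel anything". Section 6.2 has a similar line: "Patients will be told that different doses of TENS are being tested". Neither names an arm.
- After a sentence on blinding the statistician and the assessor, it says that participants will receive "the same set of instructions as those in active TENS with the addition of a statement that two TENS are being tested".

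The synopsis (Methodology) says "Participants will be blinded to the type of TENS they receive", and section 4 calls the trial double-blind. Section 4 also sets the blinding check: "Participants will be asked if they believed their TENS unit was functioning properly". The SAP lists blinding fidelity, measured by the TENS feedback questionnaire, among its feasibility and acceptability outcomes, and its Table 2 has a row for TENS blinding.

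**The concern.** An addition to the active group's instructions is, in plain grammar, something the active group does not get. An operative sentence on what staff say to participants therefore prescribes a script that depends on the arm, in a trial whose participants are meant to be blind to the type of TENS.

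Two things would be at stake if it were followed. The first is the blinding check. A participant told that two kinds of TENS are under test has a reason to wonder which one they hold, and a participant not told this has less. Their answers on whether the unit worked would then come from differently prepared groups. The second is the set of effect estimates. Section 8.1 plans effect sizes with 95% confidence intervals, and section 2.2 intends the data to inform the sample size of a definitive trial. A difference in expectation between arms would be carried into those estimates.

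**Working it through.** No figure in the plan depends on this sentence, so the check is a comparison of texts and a count of contrasts.

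**1. Who receives the addition?** The sentence compares its participants with those in active TENS. A group is not compared with itself, and the sentence sits in the placebo text, so its participants are the placebo participants. The literal result is: placebo instructions = active instructions + one statement.

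**2. Is that consistent with the rest of the plan?**

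| Place | What it implies |
|---|---|
| Section 4, opening of the Placebo TENS text | Same instructions in both arms |
| Section 4, dosage disclosure; section 6.2 | A disclosure is made; no arm is named |
| Section 4, sentence at issue | An extra statement for placebo only |
| Sections 6.1.1 and 6.2.1, treatment schedules | Nearly identical instructions for use |
| Section 6.2.2 | Attachment instructions alike; silent on the disclosure |
| Synopsis, Methodology | Participants blind to type of TENS |

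Only the sentence at issue separates the arms. No other visible text withdraws it or says that all groups hear the statement.

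**3. Could it be carried out as written?** Yes. Under Visit 2, "After this visit eligible participants will be randomized". Device instructions come at Visit 3, after allocation, and the visit table lists them separately for each group. A different script by arm is possible even if everyone heard the same thing at consent.

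**4. Which analyses would be touched?** The SAP (Section 3, Framework) names five between-group contrasts: three against Placebo TENS, and PE+TENS against each of two other groups.

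| Contrast | Active against placebo TENS? |
|---|---|
| TENS v Placebo TENS | Yes |
| PE+TENS v Placebo TENS | Yes |
| PE+Placebo TENS v Placebo TENS | No, both placebo |
| PE+TENS v PE+Placebo TENS | Yes |
| PE+TENS v TENS | No, both active |

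Three of five are affected. Two of these compare groups at the same education level. The third, PE+TENS v Placebo TENS, also differs in education, but a script difference would enter it just the same. In the other two contrasts both groups would have had the same script.

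**5. Size and direction.** The documents do not link what participants are told to any shift in absolute claudication distance or in the blinding answers. The direction is also open: the statement might raise doubt about the unit, or it might make a lack of sensation seem normal. Neither size nor direction can be derived.

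**The case against.** The strongest reply is that the rest of the plan points to one script. The dosage disclosure is given for blinding and names no arm, the treatment schedules match, and the opening of the placebo text promises the same instructions. At consent, "The Research Nurse will explain the exact nature of the study in writing, provision of patient information sheet, and verbally", and this comes before randomisation. If the information sheet tells every participant that more than one form of TENS is under test, the added statement repeats what both arms already know. Consent material is outside the review copy, so its absence cannot be held against the plan. All of this stands as evidence of intent and limits the likely harm. It does not change what the sentence tells staff to do.

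Several stronger readings are tempting but not supported:

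- *The scripts differed in practice, or blinding failed.* The documents show a sentence, not conduct.
- *Active participants were not told, because section 6.1 has no disclosure.* Section 6.1 covers settings, schedule, rationale and attachment. Its silence proves nothing about what participants hear.
- *The plan contradicts itself by mentioning both different dosages and two TENS.* The two are compatible, since there are two settings. Choosing one phrase is tidier, but this is not an error.
- *The false positive rate is inflated by a known amount.* Any such figure would need an assumed expectation shift that the documents do not supply. A t-test calculation would also not match the rank tests and analysis of covariance named in section 8.3. The strong placebo effect cited in section 1.2 justifies a placebo control but does not size a script difference.

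It is also fair to say that the gain is modest. Active users set a stimulation they can clearly feel, while placebo units run at about 6 mA. A common script leaves that difference in sensation in place.

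**Conclusion.** The point holds as a minor wording error in an operative procedure, not as a criticism of a design choice. Read literally, section 4 prescribes a placebo-only statement, against its own promise of identical instructions and against participant blinding. If followed, it could make the blinding answers non-comparable between arms and could bias three of the five between-group contrasts, by an amount and in a direction that cannot be estimated from the documents. The consequence is limited further because section 8.1 says that clinical differences are not the main purpose of this feasibility trial.

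The conclusion rests on the grammatical reading of one sentence and on the absence of any visible correction. It assumes nothing about what staff said. If the information sheet already makes the disclosure to everyone, little beyond the faulty sentence remains.

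**What to change.** Replace the sentence in section 4 with wording such as: *All participants in all four groups receive one identical scripted statement: that TENS is being tested at different doses, and that some doses may not be felt although the device is working.* All four groups receive an active or placebo unit, so the statement applies to everyone. Check that it agrees with the participant information sheet. If the sheet already says this to all participants, only the protocol sentence needs correcting.

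The cost is one sentence of protocol wording. Sample size, visits, devices and analysis stay as they are.

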#### 6.1 Active TENS:

A MTR+ Dolito TENS machine (EME Service Ltd., Manchester, United Kingdom) calibrated to 120Hz, 200 $\mu$ s, and patient-determined intensity of “strong but comfortable.”

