Measure participant's retention throughout the trial and reasons for withdrawal
Monitor, record, manage and follow-up defined adverse events in all groups
Measure uptake of intervention (log of TENS use and attendance at education) and acceptability of these interventions via a questionnaire
Measure blinding fidelity via TENS feedback questionnaire
Outcome completion rate – number of day activPAL is worn at each outcome time point.

Efficacy outcomes

Measurement will be obtained at baseline, following six weeks intervention and at 3 months follow up

Primary efficacy outcomes

Treadmill assessed Absolute Claudication Distance (ACD) (cm).

Secondary efficacy outcomes will include:

Physical activity capacity secondary outcomes

Treadmill assessed Initial Claudication Distance (ICD), assessed by a treadmill exercise using the Gardner treadmill protocol.¹⁹ Measurement will be obtained at baseline, following six weeks intervention and at 3 months follow.

Daily physical activity. We shall specify 3 days activPAL data at each measure as minimum for including patient activPAL data in the efficacy analysis. However, activPAL were time (number of day worn) will be also be reported as part of the feasibility analysis. For secondary efficacy analysis, activPAL data outcomes: total number of **i**) steps; **ii**) upright events; **iii**) walking events; **iv**) Event-based claudication index (ratio of walking events to upright events) participants undertake in a day.²⁰

PROM secondary outcomes

Disease specific quality of life will be as assessed using the Intermittent Claudication Questionnaire (ICQ).

Generic quality of life via the SF-36;

Pain quality will be recorded using the McGill Pain Questionnaire (MPQ) 5 minutes after every treadmill test.

Average Pain intensity in the past 7 days will be recorded using a Visual Analogue Scale

Illness beliefs and psychosocial determinants of health and behaviour will be recorded using the Illness Perception Questionnaire (IPQ), Geriatric Depression Scale (Short Form) (GDS-SF) and the Pain Self-Efficacy Questionnaire (PSEQ).

Qualitative Experience outcome

Analysis Methods

Feasibility and qualitative data analysis

Descriptive statistics will be used to characterize the groups at baseline and to present the feasibility outcomes.

Outcomes related to experience and perception via focus groups will be analysed by framework analysis.

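### The only blinding question described asks whether the TENS unit worked, not which setting the participant thought they had, so marked unblinding could go undetected

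*Protocol*

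**What the plan says.** Protocol section 4 (Interventions, Placebo TENS) sets the time and the question: "Blinding will be assessed at the end of the intervention period", followed by "Participants will be asked if they believed their TENS unit was functioning properly". The same paragraph gives the script. Participants hear that several dosages are under test, "some of which they might not feel anything even though the device is working". Their instructions match those of the active arm, "with the addition of a statement that two TENS are being tested". Section 6.2 adds that the placebo unit is the same model, set to about 6 mA: "This will allow the unit to be switched on with the appearance of a working unit". The active unit (section 6.1) is set to an intensity that the patient chooses as strong yet tolerable.

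The SAP lists blinding among the data to be collected (Section 3, Trial design) and among the feasibility outcomes in Section 6: "Measure blinding fidelity via TENS feedback questionnaire". Table 2 has a row for TENS blinding with nothing specified under it. The Framework paragraph plans descriptive summaries of the feasibility and acceptability data, including TENS feedback. The questionnaire items are not reproduced. Neither document describes a treatment guess, a blinding index or a criterion for judging whether blinding held.

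The timing differs between the documents. The protocol places the assessment at the end of the intervention. The SAP (Timing of outcome assessments) places it when the patient leaves the study. By the study schedule, that can be visit 4, visit 5 or the focus group.

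**The concern.** A blinding check has to ask what participants believed about their allocation. The question described asks about device function, and the script gives participants a reason to say 'yes' whatever they have inferred. Someone who feels little, concludes that they hold the weaker setting and accepts the script can truthfully say that the unit worked. So can someone who feels strong stimulation and concludes the opposite.

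The stake is a conclusion this feasibility trial exists to reach: whether this placebo is credible enough for a definitive trial. The two conditions may feel different, and the devices are used daily for six weeks. ACD depends on how long the participant is willing to walk in pain, and the questionnaires are self-reported. A blinded treadmill assessor does not protect these outcomes from participants' expectations.

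**Working it through.** **Inputs.** Protocol section 8.7 gives 80% power, two-sided 5%, an effect of 1.0 SD, 16 per group, 20% attrition, 20 recruited per group and 80 in total. The documents give no answer rates for the blinding question, so those below are assumptions.

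**Step 1: reproduce the plan's numbers, used here only as denominators.** n = 2 × (1.960 + 0.842)² / 1.0² = 15.7, so 16 per group. Then 16 / (1 − 0.20) = 20, and 4 × 20 = 80. (A t-based calculation gives 16.7, so 17; this does not affect the point.) Each TENS condition pools two groups: 2 × 16 = 32 completers, or 2 × 20 = 40 with no attrition.

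**Step 2: what each question can tell apart.**

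| Participant | Function question | Treatment guess |
|---|---|---|
| Placebo, allocation not known | yes | either, or don't know |
| Placebo, correctly inferred, accepts the script | yes | weaker |
| Placebo, correctly inferred, doubts the device | no | weaker |
| Active, allocation not known | yes | either, or don't know |
| Active, correctly inferred | yes | stronger |
| Either arm, faulty unit | no | any |

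'Yes' covers both knowing and not knowing. 'No' mixes disbelief with device faults.

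**Step 3: how far a between-arm difference could still reveal unblinding.** Suppose every participant knows their allocation, all active participants answer 'yes', and a share q of placebo participants answer 'yes'. Fisher's exact test serves only as a yardstick for a visible difference; the SAP plans no test. With k 'no' answers, all under placebo, p = 2 × C(32,k) / C(64,k).

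- k = 5: 2 × 201,376 / 7,624,512 = 0.053
- k = 6: 2 × 906,192 / 74,974,368 = 0.024

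So 26/32 or fewer placebo 'yes' answers give p<0.05. At 40 v 40 the same calculation gives 34/40 or fewer. Summing binomial probabilities gives the chance of p<0.05:

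| q | 32 v 32, all active 'yes' | 40 v 40, all active 'yes' | 32 v 32, 90% of active 'yes' |
|---|---|---|---|
| 0.95 | 0.5% | 1.4% | 2.3% |
| 0.90 | 9.4% | 20.6% | 1.1% |
| 0.80 | 64.0% | 83.9% | 10.9% |
| 0.70 | 94.9% | 99.1% | 41.1% |
| 0.50 | about 100% | about 100% | 93.5% |

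Unblinding is complete in every row. Only willingness to call the device functional changes.

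**Step 4: a treatment guess in the same situation.** Arm-specific index = (correct − incorrect) / n = (32 − 0) / 32 = +1.0 in each arm, whatever q is.

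**Step 5: precision of the index near 0 if everyone guesses.** Half-width = 1.96 × 2 × √(0.25/n). For n = 32 this is 1.96 × 0.177 = 0.35; for n = 40 it is 1.96 × 0.158 = 0.31. An index of 0.35 corresponds to (1 + 0.35)/2, about 67% correct guesses. An interval computed among guessers only would be wider if some answer 'don't know'.

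**The case against.** The strongest defence is that belief in a working device is exactly what the placebo method tries to create, so the question is a fair credibility check. If many placebo participants said 'no', Table 2 would show it by arm, and Step 3 confirms that such an excess is often visible at q = 0.80 or below when all active participants answer 'yes'. Units are calibrated and checked before issue, and the device records its own use, so faults should be few and partly traceable. This stands: the question is insensitive, not useless. A reader might infer that it must return the same answers in both arms whether blinding held or failed. That would need nearly all placebo participants to accept the script, and the documents do not say that they will.

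The questionnaire's items are also unpublished. A reader might infer that no guess is asked anywhere. The documents do not establish this; they show only that none is described, and that the protocol names a different question.

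No passage says that the placebo current cannot be felt, only that participants might feel nothing, so the extent of unblinding is unknown. The protocol cites earlier trials for this placebo method, which cannot be checked here.

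Finally, a guess after six weeks is not a pure measure of blinding, because it also reflects perceived benefit. This stands, and it is why the reason for the guess should be recorded.

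**Conclusion.** The question described cannot, by itself, show that blinding held. Marked unblinding could go undetected, and a visible difference would measure doubt about the device rather than knowledge of allocation. How likely a miss is depends on an unknown answer rate. At 32 v 32, with complete unblinding and all active participants answering 'yes', the chance of p<0.05 runs from 0.5% (q = 0.95) through 64% (q = 0.80) to 95% (q = 0.70). These figures illustrate the mechanism; they do not predict this trial.

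A reader might go further and infer that a fully unblinded trial would be reported as blinded. The documents do not support that: they set no criterion for calling the trial blinded and plan only descriptive summaries. The missing analysis is itself part of the gap.

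The change is worth making because blinding fidelity is a stated outcome. It affects neither the sample size nor the analysis of ACD.

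**What to change.** 1. Add a treatment guess to the questionnaire, worded only with what participants have been told. For example: 'Two TENS settings are being tested. Which do you think you had: the stronger, the weaker, or don't know?', followed by the main reason (sensation, change in symptoms, other). Avoid the word placebo unless participants have already been given it; the passages on the script do not show that they have. Make clear in the protocol that both arms hear the two-TENS statement, since the current sentence can be read as applying to the placebo arm only.
2. Keep the function question as a device-fault and credibility check.
3. Ask both questions of all participants at one fixed time, reconciling the protocol's end of intervention with the SAP's study exit. If they are asked before the 3-month visit, neutral wording matters more, because some participants continue.
4. In the SAP, report guess (including 'don't know') by actual TENS allocation, pooled over education, with an arm-specific blinding index such as Bang's and its 95% CI.
5. If a guess item already exists, name it and state its analysis; steps 3 and 4 still apply.

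The cost is one short item with its reason, a sentence or two in the SAP and a protocol clarification. No additional participants are needed.
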